10.1.2 Biomarkers Specific for Small Cell Lung Cancer

The second correlative study will propose correlative translational studies to investigate known promising circulating markers in the plasma in small cell lung cancer. These studies will utilize the standard ELISA assay, and will be performed at the University of Rochester Cancer Center in the laboratory of [REDACTED]

Rationale: Several serum/plasma markers have been found promising in the prognostic value for small cell lung cancer. These include neuron-specific enolase (NSE), carcinoembryonic antigen (CEA), BB isoenzyme of creatine kinase (CK-BB), angiogenic factors Interleukin 8 (IL-8) and Vascular Endothelial Growth Factor (VEGF). There are also new markers worth investigation, which include the stem cell factor (SCF), granulocyte-macrophage-colony stimulating factor (GM-CSF), and tumor hypoxia marker osteopontin. Background information of these serum/plasma biomarkers is briefly summarized as follows:

Carcinoembryonic antigen (CEA): A number of reports suggested that CEA elevations are more prevalent in SCLC patients with extensive disease (40%-65%) than limited stage (0-

38%) [30, 31]. Some reports suggested a prognostic value for monitoring response to chemotherapy and predicting disease recurrence [32].

Neuron-specific enolase (NSE): SCLC is a neoplasm with neuroendocrine origin. Serum NSE is thought to be the most sensitive tumor marker of SCLC at the time of diagnosis. While one study reported a correlation of NSE with disease extent and disease outcome [33], many other reports confirmed that NSE was a strong independent prognostic factor for complete response, remission duration and overall survival [34, 35]. In a multivariate analysis, NSE, followed by performance status and serum albumin, was the best independent predictor for survival [36].

BB isoenzyme of creatine kinase (CK-BB): CK-BB is also a neuroendocrine marker. It was found to have the best correlation with regard to predicting response and survival when compared with NSE and CEA in the same cohort of patients [33].

Interleukin-8 (IL-8): Tumor angiogenesis is one of the most important biologic features related to tumor growth and metastasis. IL-8 is a cytokine marker with angiogenic property and has been found in at least one study that the serum level was significantly increased in SCLC patients compared with healthy controls [37].

Vascular Endothelial Growth Factor (VEGF): VEGF is considered the most potent angiogenic factor in promoting growth of tumor vasculature. Tumor expression of VEGF as well as circulating VEGF have been demonstrated to be of prognostic significance, correlating with tumor progression or patient survival [38-40]. One study showed that high pretreatment serum VEGF level was an adverse prognostic factor for survival independent of tumor stage [40], other studies found a correlation between serum VEGF level and stage progression [41].

Stem cell factor (SCF): SCF, the ligand for c-Kit receptor, has been implicated in the regulation of angiogenesis in hematopoietic and nonhematopoietic malignancies. At least 70% of SCLC tumor specimens and cell lines co-express SCF and c-Kit [42]. SCF/c-Kit pathway is functional in an autocrine or paracrine fashion in SCLC [43-46]. One study found that patients with SCLC have significantly increased levels of SCF when compared with the control [47].

Granulocyte-macrophage-colony stimulating factor (GM-CSF): GM-CSF is a known cytokine for the proliferation of hematopoietic cells. At least one study found significantly increased levels of GM-CSF in patients with SCLC when compared with the control [47].

Osteopontin (OPN): Tumor hypoxia has been shown to affect the malignant progression of tumors, as well as being one of the leading causes of cancer resistance to chemotherapy and/or radiotherapy. Studies have indicated that hypoxia increases tumor invasiveness and dissemination in human solid tumors [48, 49]. Hypoxia also regulates VEGF expression by enhancing transcription of the VEGF gene and by stabilizing its mRNA. It is now clear that the transcription factor hypoxia-inducible factor (HIF) 1 α is the major regulator of VEGF transcription in response to hypoxia [50, 51]. Molecular laboratory work has suggested that OPN may be linked to tumor hypoxia and plasma OPN level was increased in patients with hypoxic tumors of head and neck, and the levels correlated with clinical outcomes [52].

In addition to analyzing the small cell lung cancer specific biomarkers as described above, we will also include two additional groups of proteins. First, we will assess factors that we have already established to be modulated by radiotherapy or endothelial damage, including VEGF, soluble VEGFR-2, and E-selectin [53-55]. The second set of factors will be proangiogenic cytokines that may contribute to resistance by promoting the proliferation and survival of tumor endothelial cells. First, several selected proangiogenic cytokines

known to play a role in angiogenesis in lung cancer, including VEGF, basic fibroblast growth factor (bFGF), transforming growth factor α (TGF- α), and interleukin-8 (IL-8).

Objectives: The objectives of the correlative studies for small cell specific circulating markers are:

1. To investigate the value of the published markers specific to small cell lung cancer in the large phase III clinical study setting. We will analyze the baseline biomarker profile, changes in the profile during treatment at the time of recurrence to correlate with the response rate, progression free survival, and overall survival of these patients.
2. To compare the differences in the biomarker profile between the two treatment arms.

Hypotheses

1. Circulating biomarkers may have prognostic or predictive value of small cell lung cancer.
2. The differences in circulating biomarkers between the two treatment arms may reveal information correlating with efficacy of treatments.

Method for the ELISA Assay

ELISA is a standard laboratory analytical method for protein quantification in the plasma or serum (R&D Systems, Minneapolis, MN). This assay requires a significant volume of sample (100-200 μ l) for each biomarker. The ELISA assay has high sensitivity and high precision, and thus has been the standard assay of cytokine measurement.

10.1.3 ProGRP as a Marker to Monitor the Response to Therapy and for the Prediction of Relapse Following Therapy

The goal of this correlative study is to evaluate the performance of proGRP as a biomarker in SCLC lung cancer. In addition, this study will provide an opportunity to better understand the role proGRP to monitor the response to therapy and the relapse following therapy.

This correlative study will be performed at an Abbott Center of Excellence, which are clinical laboratories chosen for their expertise in assay evaluation and biomarker evaluation. The target Center of Excellence for this study is the clinical laboratory at Johns Hopkins run by [REDACTED]. This is a CLIA approved laboratory.

Rationale: Gastrin releasing peptide (GRP) is a gut hormone and is widely distributed in the mammalian gastrointestinal tract, nervous system and pulmonary tract. GRP is an autocrine growth factor, and binding of GRP to cell surface receptors leads to altered expression of the c-fos oncogene and cell proliferation.

Tumor tissues from SCLC patients show amplification of GRP mRNA and protein. However, serum GRP was not useful for clinical diagnosis due to its very poor stability in specimens. In 1994, an assay to detect a ProGRP fragment (residues 31-98) in serum was developed because the molecule was more stable than GRP. Approximately two thirds of patients with SCLC have elevated concentrations of ProGRP in their serum. The clinical usefulness of the ProGRP 31-98 measurements has been widely reported for the diagnosis, the prediction of prognosis, and the monitoring of treatment in patients with SCLC (94). Neuron-specific enolase (NSE) has been also used as a tumor marker of SCLC, however compared to NSE, ProGRP has relatively high sensitivity, specificity and early recognition of relapse in patients with SCLC (95). The progression of SCLC in patients under therapy in small cohorts of 44 patients and 66 patients has been reported. The majority of patients under treatment showed decreased levels of ProGRP, particularly those with objective responses. The sensitivity for detection of responses ranged from 70-79.7% and the addition

of NSE was found to improve sensitivity to 85.9%. The trend of ProGRP in patients with progressive disease was generally upward.

There have been many publications over the years showing the clinical utility of proGRP as a marker for SCLC. Some important reviews of the literature (96-98) have demonstrated the proGRP was the best tumor marker in his evaluation for patients with SCLC. In addition, the National Academy of Clinical Biochemists Practice Guidelines and Recommendations for the Use of Tumor Markers in Lung cancer recognize the clinical use of proGRP in the differential diagnosis of lung masses and in the monitoring of therapy response and detection of recurrent disease (Stieber et al, manuscript in review, Clin Chem.) From the multiple reports, it is clear that proGRP is a valuable tumor marker for SCLC, but it has not been validated in a prospective study.

Objectives: The objectives of this correlative study are:

Primary:

- 1) To evaluate the correspondence between increases in plasma ProGRP concentrations and disease progression/recurrence.

Secondary:

- 1) To evaluate the potential for plasma ProGRP concentrations at baseline, after each cycle of chemotherapy and at first evaluation following completion of chemotherapy to predict PFS and OS.
- 2) To evaluate the correspondence between longitudinal decreases in plasma ProGRP concentrations and clinical response.

Exploratory:

- 1) To evaluate novel biomarkers for their ability to improve correspondence and prediction of response to therapy in patients with SCLC. This may involve the use of multiple biomarkers, including ProGRP, in conjunction with the biomarkers specific for small cell lung cancer being studied by [REDACTED]

Hypotheses

- 1) ProGRP will have a relatively high sensitivity, specificity and early recognition of relapse in patients with SCLC. An increase in proGRP level may be detected approximately a month prior to clinical evidence of relapse
- 2) The majority of patients under treatment will show decreased levels of ProGRP, particularly those with objective responses. NSE and proGRP together may be a combination of biomarkers that most accurately predicts response to therapy.

Methods

Plasma is the sample type that will be used for the assay. The plasma levels of ProGRP will be assayed on the ARCHITECT ProGRP assay. The ARCHITECT ProGRP assay is a automated two-step, sandwich format. Analyte capture is with paramagnetic microparticles coated with two mouse monoclonal anti-ProGRP 31-98 antibodies: 3G2 (amino acids of ProGRP 84-88) and 2B10 (amino acids of 71-75), which can capture the C-terminal side of ProGRP 31-98. Detection of the ProGRP analyte microparticle complex is by an acridinium labeled mouse monoclonal antibody conjugate. The mouse monoclonal antibody of 3D6-2 can capture the N-terminal side of the protein (amino acids of ProGRP 40-60). Exposing the reaction mixture to on-board trigger reagents containing peroxide at alkaline pH causes the release of light that is proportional to the ProGRP level in the specimens, calibrators, or controls. The ARCHITECT ProGRP assay calibrators range from 0 to 5 000 pg/mL (0, 20, 80, 320, 1 250, and 5 000 pg/mL). A 1:10 autodilution is used to extend the measurable

range up to 50 000 pg/mL. ARCHITECT ProGRP control concentrations are 40, 160, and 2 500 pg/mL. To minimize the risk of interference from human-anti-mouse antibodies, heterophilic antibodies, and rheumatoid factor, blocking agents and murine mAbs of different isotypes are used in the assay. Furthermore, the F(ab')₂ portion of the antibody with Fc portion eliminated by pepsin digestion is used to produce the conjugate. The assay is fully automated and measurement is completed within 30 minutes with 200 tests / hour throughput.

The ARCHITECT ProGRP assay is available CE Marked for sale in Europe and approved for sale in Japan and has been fully validated. The performance was defined by multisite studies in Japan, Germany and the US. These results are in press (Clinical Chemistry and Laboratory Medicine) and is summarized as follows: The total precision %CV for 9 analyte levels was between 2.9-5.7. The analytical sensitivity of the assay was between 0.20-0.88 pg/mL. The functional sensitivity at 20%CV was between 0.66-1.73 pg/mL. The assay was linear up to 50 000 pg/mL with a 1:10 autodilution protocol. The calibration curve was stable for 30 days. The comparison with Fujirebio microtiter plate EIA ProGRP assay gave a slope of 0.93 and a correlation coefficient (r) of 0.99. No interference was seen with chemotherapeutic agents or common interfering substances (bilirubin, hemoglobin, triglycerides, high protein, etc.).

The goal of this correlative study is to obtain information on the clinical value of ProGRP in the US to support an FDA submission and to provide information on its clinical utility to the medical professionals responsible for treating patients with SCLC.

10.2 Health Related Quality of Life (CALGB 70702)

As early as 1956, the World Health Organization defined quality of life as “a complete physical, mental and social well-being and not merely the absence of disease or infirmity” [56]. Thirty-four years later, the definition had not changed, with the major areas of quality of life consisting of physical/occupational status, psychological state, social interaction and somatic sensation [57]. These areas may be the most likely to be impacted by different cancer treatment regimens, with disease factors and treatment toxicity affecting physical symptoms and functioning, and consequently, psychological state and social functioning.

In this dose-response thoracic radiotherapy trial in limited small cell lung cancer, three different doses are being compared in terms of their response rates, failure-free survival and toxicity: 70 Gy (2 Gy once-daily for 7 weeks), 61.2 Gy (1.8 Gy once-daily for 16 days followed by 1.8 Gy twice daily for 9 days), and 45 Gy (1.5 Gy twice-daily over 3 weeks). In Turrisi's study [5], the major increased toxicity for the hyperfractionated dose of 45 Gy in 3 weeks was a doubling of the severe (grades 3 and 4) acute esophagitis rate. Esophagitis typically limits oral intake, requires a change in diet (soft-liquid), may necessitate frequent IV hydration and may be associated with significant fatigue, decreased activity and functioning (and possibly not be able to work) and pain. The impact of these side effects on patient's psychological state and potentially social interaction for those with esophagitis can be significant. In Mehta et al.'s [58] phase II trial, 30 non-small cell lung cancer patients were administered hyperfractionated accelerated radiotherapy: 54 Gy over 12 consecutive treatment days, with three fractions administered daily with a 6 hour interval between fractions. Of the 28 patients who completed treatment, 22% had grade 3 and 4 esophagitis [58]. All esophagitis resolved after treatment. However, in Auchter et al.'s [59] quality of life study of these patients, there were statistically significant declines in physical and functional well-being at treatment completion, with a return to baseline levels occurring at 4 weeks post-treatment completion. Emotional state improved by the time of treatment completion and at 4 weeks post-treatment completion. In Bonner et al.'s [60] phase III trial involving limited stage small-cell lung cancer, while there were no differences

in overall progression rates or overall survival between the once-daily thoracic radiation (50.4 Gy) and twice-daily (48 Gy twice-daily with a two week break after 24 Gy) dose groups, those who received the twice-daily dose had significantly greater esophagitis (grade 3 or greater) than those receiving the once-daily dose. However, there were no significant differences in quality-adjusted life years between patients receiving once-daily versus twice-daily thoracic radiation [61]. In a study by Bailey et al. [62], non-small cell lung cancer patients were randomized to continuous hyperfractionated accelerated radiotherapy (54 Gy, 1.5 Gy three times daily for 12 days) or conventional radiotherapy (60 Gy: 2 Gy in 30 fractions for 6 weeks). Apart from patients in the hyperfractionated accelerated group reporting transient pain on swallowing and heartburn, there was little difference between the two arms of the trial. To date, there is no prospective, longitudinal data on the impact of hyperfractionated accelerated dose at the level proposed in this study on patients' quality of life.

10.2.1 Objective: To compare patients' quality of life between these regimens in terms of their physical symptoms, physical functioning and psychological state

Hypothesis A: Patients in the hyperfractionated accelerated dose (45 Gy) group will experience worse lung cancer specific physical symptoms and physical functioning, as measured by the FACT TOI (Trial Outcome Index)-Lung Cancer and FACT-Esophageal Cancer Eating and Swallowing Indices, than those in the high dose daily (70 Gy) and concomitant boost radiotherapy (61.2 Gy) groups when all RT has been completed in each arm of the study at 12 weeks after the start of radiation therapy. This hypothesis will be revised to reflect the change in the research design due to the elimination of one of the experimental arms (high dose daily or the concomitant boost radiotherapy arm), due to greater toxicity.

Hypothesis B: Patients in the hyperfractionated accelerated dose (45 Gy) group will experience worse esophagitis (measured by the ECOG Acute Esophagitis Scale and difficulty swallowing item), and as a consequence worse psychological state, (measured by the Hospital Anxiety and Depression Scale), and lower quality-adjusted life years (measured by the EQ-5D) than those in the high dose daily (70 Gy) and concomitant boost radiotherapy (61.2 Gy) groups when all RT has been completed in each arm of the study at 12 weeks after the start of radiation therapy. This hypothesis will be revised to reflect the change in the research design due to the elimination of one of the experimental arms (high dose daily or the concomitant boost radiotherapy arm), due to greater toxicity.

Hypothesis C: Patients in the high dose daily 70 Gy arm of the study will experience greater treatment inconvenience (measured by a single item developed for this study), than those in the other two arms of the study, due to having to come into clinic for 7 weeks, the longest duration of the three arms. If the 70 Gy arm is eliminated due to greater treatment toxicity, than this hypothesis will be revised to reflect that those in the 61.2 Gy arm will experience greater treatment inconvenience than those in the 45 Gy arm, due to having to come into clinic for 5 weeks.

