EQ-5D is a measure of health status for use in evaluating health and healthcare. It provides a simple descriptive profile of 5 functional dimensions and generates a single utility value for health status on which best imaginable health is assigned a value of 1 and worst imaginable health a value of 0. Thus, the index can be used to obtain a utility for these dimensions for use in economic analyses. The EQ-5D has been specially designed to complement other quality of life measures such as the SF-36, or cancer-specific measures. Descriptively, the EQ-5D consists of 5 dimensions, mobility, self-care, usual activity, pain/discomfort, and anxiety/depression. Each dimension has 3 levels designated simply as “no problem,” “some problem,” or “extreme problem,” with patients checking the level most descriptive of their current level of function on each dimension. Five dimensions, each with three levels, yield 243 possible distinct health states comprising the classification system. The classification system has been assigned different standardized scores derived through population-based samples of respondents who assign values to subsets of the 243 states using the anchoring labels noted above [79]. A set of valuation weights has thus been derived from a U.S. sample more recently [79, 80]. The Agency for Healthcare Research and Quality has funded a study to develop definitive weights. EQ-5D is designed for self-completion by patients and has been used extensively in mailed surveys. It is cognitively simple, taking no more than a few minutes to complete. Quality-adjusted life years can be calculated from using the EQ-5D in conjunction with a utility scale of health states.

- Treatment Inconvenience (Form C-1735)

The different treatment arms have different dose schedules for different lengths of times, which may impact the satisfaction with treatment due to the inconvenience posed. Therefore, an item will be added as to the inconvenience of going for therapy at the different dose schedules.

- Sociodemographic Characteristics (Form C-187)

Demographic data, including education, marital status, employment and household composition, will be obtained at baseline only using the CALGB Background Information Form [81] (CALGB Form C-187). Age, gender, and ethnicity will be obtained upon patients' registration to the study.

- QOL Assessment Form (Form C-419, revised)

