
Secondary Endpoints
 
Esophagitis
	
Hypothesis B: At 12 weeks after the start of XRT, patients in the 45Gy arm will experience worse esophagitis than those in the high dose daily (70Gy) and concomitant boost RT (61.2 Gy) groups.
	
ECOG Acute Esophagitis Scale
 
Difficulty swallowing
	
Dichotomized or ordinal scores/outcomes
 
Chi-square test; Logistic regression; Nonlinear mixed effect or generalized linear model with generalized estimating equations using log or multi-log link.

Psychological state
	
Hypothesis B: At 12 weeks after the start of XRT, patients in the 45Gy arm will report a worse psychological state than those in the high dose daily (70Gy) and concomitant boost RT (61.2 Gy) groups.
	
Hospital Anxiety and Depression Scale (HADS)
	
Continuous scores/outcomes
 
T test; Analysis of covariance; Line mixed effect model or general linear model with generalized estimating equations

Quality-adjusted Life Years (QALY)
	
Hypothesis B: At 12 weeks after the start of XRT, the QALY of those in the 45 Gy will be worse than those in the high dose daily (70Gy) and concomitant
	
EQ-5D
	
Quality adjusted time to event variable/outcome
 
Generalized log rank test for QALY data

	boost RT (61.2 Gy) groups.		
Treatment Inconvenience	Hypothesis C: At 7 weeks after the start of XRT, treatment inconvenience will be greatest for those receiving 70Gy QD in 7 weeks.	Single item developed for the study	Dichotomized or ordinal scores/outcomes Chi-square test; Logistic regression; Nonlinear mixed effect or generalized linear model with generalized estimating equations using log or multi-log link.

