The following assumptions are made in the power calculations: (1) Based on the literature and previous CALGB studies, we expect that at least 80% of eligible patients who register to the companion will complete the HRQOL assessments at both baseline and 12 weeks after the start of radiation therapy. That is, of the 394 eligible patients on the companion study, 150 patients in the two remaining study arms and 15 in the discontinued study arm will have complete HRQOL assessments at both baseline and 12 weeks after the start of radiation therapy; (2) Within each set of hypothesis (A, B, C), Type I error will be controlled at the level of 0.05. The Bonferroni method is used to address the issue of multiple comparisons for simplicity and reasonable performance with a small number of comparisons; and (3) Two-sided tests will be used.

Hypothesis A

Three planned comparisons will be made to address Hypothesis A. The total TOI score from FACT TOI, the eating score and the swallowing score will be calculated from the FACT-Esophagus Subscale. The change scores between baseline and 12 weeks after the start of radiation therapy are of interest. A size of 150 patients with complete assessments at baseline and 12 weeks after the start of radiation therapy in each of the two remaining arms will have 85% power to detect an effect size of 0.397 s.d. unit on the scale of change score using a two group t-test at a significance level of 0.0167 (0.05/3). The effect size of 0.397 s.d. is usually associated with a moderate effect in quality of life literature.

Hypothesis B

Five comparisons will be made to address this hypothesis - ECOG esophagitis score (severe/ ≥ 7 vs moderate/ < 7), difficulty swallowing (severe/ ≥ 4 vs. moderate/ < 4), HADS depression score, HADS anxiety score, and quality-adjusted life year (QALY).

The ECOG esophagitis score ranges from 0 to 12 points. We will define patients with scores of ≥ 7 as “Severe” and score < 7 as “Moderate.” With 150 patients in each remaining arm with complete assessments at baseline and 12 weeks after the start of radiation therapy, a two group continuity corrected Chi-square test at a 2-sided significance level of 0.01 (0.05/5) will have 80% power to detect the 18% difference of the proportions of patients with severe symptoms between the two remaining study arms, assuming 35% of patients in arm 1 report severe symptoms and 17% in the other remaining arm (odds ratio of 2.625).

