We define swallowing difficulty score as 4 or 5 as “Severe” and scores 1, 2, or 3 as “Moderate.” Similar to the ECOG esophagitis score, with 150 patients in each study arm, we have 80% power to detect a 18% difference of severe swallowing difficulty between the two study arms, assuming 35% swallowing difficulty for arm 1 and 17% in the other arm.

The depression and anxiety scores of HADS are of primary interest. Consider the change score between baseline and 12 weeks after the start of radiation therapy. With 150 in each of the two remaining arms, one has 85% power to detect an effect size of 0.419 s.d. unit on the scale of change score using a two group t-test at a significance level of 0.01.

Quality-adjusted life years (QALY) is calculated as EQ-5D utility score weighted survival time. For the purpose of power calculation, consider a patient with a QALY greater than 12 weeks as “success” and less than 12 weeks as “failure.” With a size of 150 patients having EQ-5D score at baseline and 12 weeks, we have 90% power to detect a 20% difference of 12-week success rate, assuming the 12-week success rate is 65% for arm 1 (45 Gy) and 85% for the remaining experimental arm.

Hypothesis C

The different treatment arms have different dose schedules for different lengths of times, which may impact the satisfaction with treatment due to the inconvenience posed. Patients with an inconvenience rating of 1 or 2 will be defined as “Inconvenient” and those with a rating of 3 or 4 as “Convenient.” If the remaining experimental arm is arm 2 (70 Gy), with 150 patients having inconvenience measure on each arm at baseline and 12 weeks after the start of radiation therapy, a two group continuity corrected Chi-square test at a significance level of 0.05 will have 81% power to detect the 16% difference of the proportion of patients reporting treatment inconvenience between the two remaining study arms, assuming 60% of patients in arm 1 report treatment inconvenience and 76% of patients in arm 2 report inconvenience. If arm 2 is discontinued after 30 patients have been accrued to the main study, with about 150 patients in arm 1 and 15 patients in arm 2 having complete assessment at baseline and 12 weeks, we will have 74% power to detect the 30% difference of the proportion of patients reporting treatment inconvenience between the two remaining study arms, assuming 60% of patients in arm 1 report treatment inconvenience and 90% of patients in arm 2 report inconvenience.

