It is expected that a proportion of quality of life data collected at follow-up assessments will be missing due to various reasons, including failing health of patients. However, the percentage is expected to be less than 10% above and beyond that missing due to death. If the dominant missing mechanism is missing completely at random (MCAR) above and beyond the effect of study condition assignment, then the results based on complete data analysis will be unbiased. However, sensitivity analyses using different statistical methods and assuming different missing mechanisms (MCAR, MAR and NMAR) will be used to evaluate the robustness of main study findings from multivariate data analyses.

The quality-adjusted overall survival will be calculated for each study arm based on the utility score from EQ-5D and the subgroup difference will be tested using the method developed by Zhao and Tsiatis [93].

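### Hypothesis B places its QALY comparison at 12 weeks, but the plan powers it on an outcome impossible within 12 weeks and analyses it as quality-adjusted overall survival, which cannot be read as a consequence of esophagitis

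*Combined protocol and SAP*

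**What the plan says.** Four places in the plan describe the QALY comparison, with different horizons.

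- **Section 10.2.1, Hypothesis B.** Patients on 45 Gy are expected to have worse esophagitis and "as a consequence worse psychological state, (measured by the Hospital Anxiety and Depression Scale), and lower quality-adjusted life years (measured by the EQ-5D"). The sentence fixes the time: "when all RT has been completed in each arm of the study at 12 weeks after the start of radiation therapy".
- **Section 15.7, opening statement of Hypothesis B.** The same hypothesis is repeated without the 12 weeks. It says only that all radiotherapy has been completed.
- **Section 15.7, Table 2.** The 12-week anchor returns: at that point "the QALY of those in the 45 Gy will be worse than those in the high dose daily (70Gy") and concomitant boost groups. The named method is "Generalized log rank test for QALY data".
- **Section 15.7, Power Analysis and Analytic Methods.** "Five comparisons will be made to address this hypothesis", and QALY is one of the five, so its Bonferroni share is 0.05/5 = 0.01. "Quality-adjusted life years (QALY) is calculated as EQ-5D utility score weighted survival time". Power is computed for the proportion with a QALY above 12 weeks: 65% on 45 Gy against 85%, 150 per arm, 90% power. The analysis itself is then described differently: "The quality-adjusted overall survival will be calculated for each study arm based on the utility score from EQ-5D", with a between-arm test and no restriction time.

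On the utility scale in section 10.2.3, "best imaginable health is assigned a value of 1 and worst imaginable health a value of 0". Section 6.2 schedules the EQ-5D at baseline and at weeks 3, 5, 7, 12, 26 and 52 after the start of radiotherapy. No planned comparison tests EQ-5D utility itself.

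**The concern.** The hypothesis concerns an acute, largely transient toxicity. Quality-adjusted overall survival is utility multiplied by survival time, and survival is the primary endpoint, designed to differ between the arms. Without a horizon, years of survival time outweigh a few weeks of reduced utility. A significant QALY result could then arise with identical utilities in both arms, while a real acute loss on 45 Gy could leave no trace.

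At stake is the interpretation of one of five alpha-bearing comparisons in a secondary quality-of-life family. An analyst who follows section 10.2.1 and Table 2, and one who follows the Analytic Methods, would test different quantities and could report opposite conclusions under the same label. The trial's primary survival analysis is not affected.

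**Working it through.** **1. The plan's own power figure.** Inputs from section 15.7: 0.65 and 0.85, n = 150 per arm, two-sided α = 0.01 (z = 2.576). The pooled proportion is 0.75.

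Power = Φ{[Δ√n − z√(2·0.75·0.25)] / √(0.65·0.35 + 0.85·0.15)} = Φ{(2.449 − 1.577)/0.596} = 92.8%.

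Reducing Δ by 1/n as a continuity correction gives 90.8%. The stated 90% reproduces.

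**2. Can that outcome occur?** Utility is at most 1, so the largest QALY within 12 weeks is 12 × 1 = 12 weeks. A value above 12 is impossible on the horizon of the hypothesis. On a longer horizon, at an assumed constant utility of 0.8, it means surviving beyond 12/0.8 = 15 weeks. With the exponential medians of section 15.3, this gives 90.1% and 92.3%. An added loss of 2 quality-adjusted weeks on 45 Gy gives 88.6% and 92.3%. Neither pair is near 65% and 85%; power is 2.8% and 7%.

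**3. Survival effect alone, all follow-up.** Inputs from section 15.3: λ₁ = ln 2/23 = 0.0301 and λ₂ = ln 2/29.9 = 0.0232 per month, accrual 72 months, further follow-up 30 months.

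P(death) = 1 − [e^(−30λ) − e^(−102λ)]/(72λ) = 0.835 and 0.757.

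Check: 303 × (0.835 + 0.757) ≈ 482 deaths, against the plan's 483.

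With equal utilities the QALY test behaves much like a log-rank test on survival, so power ≈ Φ(√(D/4)·ln 1.3 − 2.576):

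- 150 per arm (expected complete assessments): D ≈ 239, Φ(2.027 − 2.576) = 29%.
- 188 per arm (eligible companion patients): D ≈ 299, Φ(2.270 − 2.576) = 38%.

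Simulations of a log-rank test on utility-weighted time, with mean utility 0.75 and SD 0.05–0.20 in both arms, give 26–29% and 34–36%. A repeat simulation gives about 29% and 37%.

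**4. Transient loss alone, all follow-up.** With equal survival and a 0.10 loss for 12 weeks in every 45 Gy patient, the test rejects in about 1%, which is its alpha. Even a loss of 0.5 over 10 weeks in every 45 Gy patient, and none in the other arm, gives 2.0%.

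The sizes explain this. The survival effect to 8.5 years is u × [(1 − e^(−102λ₂))/λ₂ − (1 − e^(−102λ₁))/λ₁]. At u = 0.8 that is 25.9 quality-adjusted weeks. The transient loss is 0.10 × 12 = 1.2 weeks.

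**5. The answer depends on the horizon.**

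| Horizon | Survival effect only | Transient loss only |
|---|---|---|
| All follow-up | about 29–37% | about 1–2% |
| 52 weeks | 8–11% | 2% (loss 0.3 for 10 weeks, all 45 Gy patients) |
| 12 weeks | 2–3%; about 1% among those alive at week 12 | 48–100% if all 45 Gy patients and no comparators are affected; 2–51% if 35% and 17% are |

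The 12-week transient-loss figures assume utility 0.8, SD 0.2, losses of 0.1–0.5 over 6 or 10 weeks, and up to 150 per arm alive at week 12. At 12 weeks the survival effect is worth only 0.09 quality-adjusted weeks.

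**6. Power of a 12-week utility comparison.** n = 150 per arm, α = 0.01, power ≈ Φ(δ/(SD√(2/150)) − 2.576).

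- Loss of 0.10 in every 45 Gy patient and in no comparator, δ = 0.10: over 99%, 96% and 81% for SD 0.15, 0.20 and 0.25.
- Loss of 0.10 only in those with severe esophagitis, at the plan's 35% and 17%, δ = 0.10 × (0.35 − 0.17) = 0.018: about 6%, 4% and 3%.

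**The case against.** The strongest reply is that section 10.2.1 and Table 2 both put the comparison at 12 weeks, and section 15.7 names the change from baseline to week 12 as the primary interest. On that horizon survival contributes almost nothing and a transient loss can be detected. This stands: a reader might infer that the QALY comparison fails however it is run, and the documents do not support that. But they do not settle on 12 weeks either. The power calculation uses an outcome that cannot occur there, and the Analytic Methods describe overall survival.

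Other replies also have weight:

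- The EQ-5D ends at week 52, so the 29–37% assumes utilities continue unobserved for years. It is still a minority of trials.
- An acute effect need not be missed by the trial. The FACT-L TOI, eating, swallowing, esophagitis and HADS scores are all tested, with exploratory change scores at weeks 3, 5 and 7.
- The punctuation in section 10.2.1 allows QALY to be read as a parallel item rather than a consequence, and Table 2 has no causal wording. The comparison still belongs to the esophagitis hypothesis and is still tied to 12 weeks.
- The absence of a stated value for death in section 10.2.3 is not a defect to press. Utility-weighted survival time accrues nothing after death, and the section defers to published valuation weights.

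**Conclusion.** The point holds as an inconsistency of horizon. The hypothesis and Table 2 say 12 weeks, the section 15.7 restatement gives no time, the power basis requires more than 12 weeks, and the analysis is of overall survival. If the Analytic Methods are followed, a QALY difference cannot be read as a consequence of esophagitis. The design survival effect alone triggers it in roughly 29–37% of trials, and a transient loss with equal survival in about 1%.

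These figures rest on exponential survival at the design medians, a log-rank test standing in for the generalized test, mean utility 0.75 and two-sided 0.01. The utility values and losses are assumptions. The direction was the same across the ranges tried. The plan cites a trial (section 10.2) with more grade 3 or worse esophagitis on twice-daily treatment, no survival difference and no QALY difference, which fits this pattern.

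Two stronger inferences should be avoided: that a survival benefit would reliably produce a QALY result, and that a 12-week utility comparison would be well powered. The first happens in about one trial in three; the second depends on how many patients are affected.

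**What to change.** State one horizon for the Hypothesis B comparison in section 10.2.1 and, within section 15.7, in the opening hypothesis, Table 2, the Power Analysis and the Analytic Methods. Define it as EQ-5D utility accumulated over weeks 0–12 from the baseline and week 3, 5, 7 and 12 forms (equivalently, a 12-week QALY), adjusted for baseline, at the same per-comparison alpha of 0.01.

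Add a rule for early deaths, for example utility 0 after death or restriction to patients alive at week 12. Under the design assumptions about 8% (45 Gy) and 6% (70 Gy) die by week 12. Replace the power basis with one possible on this horizon, and show power for both a loss in all patients and a loss only in those with severe esophagitis.

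Report quality-adjusted overall survival separately, beside its utility and survival components, and do not attribute it to esophagitis.

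The cost is wording in the protocol hypothesis and the statistical section; the EQ-5D data are already scheduled. Accrual to the companion closed on August 30, 2017, so the sample cannot be enlarged. Power may be anywhere from about 3% to over 99% on the assumptions above, and no high figure should be claimed.
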